### **2.4.1 What is Standard of Care in this study? (Standard of Care should be described in the Purpose section of the Consent Form. You should NOT list these in the Risk section of the Consent Form.)**

This study is looking at the comparative effectiveness of two FDA-approved devices, that are both well-described in the literature for this specific operation. These devices will be used in accordance with the labeling. Patients qualify for bariatric surgery if they have a BMI of 40 or 35 with obesity-related

comorbidities (hypertension, obstructive sleep apnea, pseudotumor cerebri, hyperlipidemia, diabetes, etc). All patients undergo psychiatric screening, laboratory assessment to rule out other cause of obesity, such as hypothyroidism, esophagogastroduodenoscopy, ultrasound of their gallbladder, and multiple counseling sessions prior to scheduling surgery. Patients may choose which bariatric procedure they prefer between sleeve gastrectomy, roux-en-y gastric bypass, and gastric band placement. Once scheduled for surgery, they will present to the hospital 6th floor. They will be given one dose of 5000 units subcutaneous heparin. Preoperative antibiotics of cefazolin or clindamycin will be administered within 30 minutes of surgery start time. Patients will be placed on the operating table in the supine position with a footboard in place. Sequential compression devices will be placed on the lower extremities. General endotracheal anesthesia will be induced. The abdomen will be prepped and draped in the usual sterile fashion. A time out will be completed, verifying the correct patient, procedure, site, positioning, and special equipment prior to starting the surgery. A fenestrated bougie will be placed through the patient's mouth, into the stomach. Pneumoperitoneum will be obtained, and a trocar with a laparoscope will be inserted. The abdominal contents will be inspected for evidence of injury. Three additional trocars will be placed under direct visualization and a Nathanson retractor will be used to retract the liver. Negative pressure will be applied to the fenestrated bougie after proper positioning laparoscopically. The stomach will be inspected, and a site 4-6 cm proximal to the pylorus will be identified. A defect will be made in the greater omentum at this site close to the greater curvature of the stomach using a harmonic scalpel. Dissection will be carried along the greater curvature of the stomach to the gastroesophageal junction, taking care not to injure the spleen. Starting with a black load with and absorbable polymer membrane reinforcement on either the Covidien iDrive with reinforced Tristaple technology or the Ethicon Echilon powered stapling device with Gore Seamguard reinforcement. Typically at our institution, the Ethicon Echilon device is used more frequently simply due to availability, but all bariatric surgeons are trained on both devices. Subsequent stapler loads will be surgeon and patient-dependent. Typically Ethicon black loads will be used until the fundus of the stomach, at which point a blue load without reinforcement is used. For Covidien, the black load is typically exchanged for a purple load near the fundus. Once the sleeve is complete, the stomach will be submerged in saline, and the remnant stomach will be insufflated, looking for any evidence of air leak, which would be repaired prior to conclusion of the case. The staple line will be inspected for bleeding. The gastric remnant will be removed though a port, and the abdomen will be desufflated. Incisions will be closed with 4-0 monocryl and covered in Dermabond. Patients are kept NPO and monitored overnight with intravenous fluids. They are started on water sips the next morning and are advanced to a bariatric liquid diet if they tolerated water sips. If they have adequate pain and nausea control and are taking in adequate fluid, they are discharged home on post-operative day one. They will follow-up at week 3, week 6, month 3, month 6, and annually.

**2.4.2 What is investigational or experimental in this study? (This is not Standard of Care. You will describe this in the Purpose section of the Consent Form, and MUST list these in the Risk section of the Consent Form. The risks should be listed as: Common; Probable; and Rare.)**

The stapler used for each surgery will be randomly assigned. Neither manufacturer has proven superiority, so there is no deviation from standard of care in using different staplers. Also, the data collection, including time to reload staplers, time to complete sleeve, documentation of staple line bleeding, post-operative complications, and weight loss, is unique to this study and be recorded in a spreadsheet unique to this project.

**2.4.3 Is any part of the investigational / experimental procedure(s) you are doing Off-Label Use? (If the answer is yes, you must discuss the Off-Label Use with the HPA / RRS).**

No

**3. OBJECTIVES AND SPECIFIC AIMS:**

Primary objectives: Determine if using different brand staplers affects:

1. Time of creation of sleeve from first firing to completion
2. The percent of firings with technical difficulties
3. The time for tech to load each staple cartridge (aware of Hawthorne effect. Since both arms will be subject to Hawthorne effect, the only variable should be the stapler)

Secondary objectives: Determine if using different brand staplers affects:

1. Any bleeding after creation of the sleeve (annotating whether single or multiple interventions are required)
2. Weight loss
3. Leak rates
4. Hospital readmissions or emergency room visits (For complications including but not limited to dehydration, hemorrhage, leak, internal hernia, and pain; will annotate what complication warranted readmission)
5. Further sleeve interventions

**4. MEDICAL APPLICATION/ MILITARY RELEVANCE:**

Bariatric surgery is very common in military treatment facilities with surgical capability. Determining if a certain stapler is superior has potential to reduce complication rates, improve quality of care, decrease costs, and optimize resource utilization.

**5. BACKGROUND AND SIGNIFICANCE SECTION**

**5.1 Literature Review and Preliminary Data and/or Findings:**

Demonstrate that you have done a comprehensive literature search that includes the following:

**a. Date of Search:** 02 Sept 2015

**b. Search terms used:** Laparoscopic sleeve gastrectomy, stapler, bariatric surgery, Covidien, Ethicon

**c. Databases Searched:** PubMed, Google Scholar

In 2011 and 2012, it was found that 34.9% of Americans were obese . As a result, many patients will turn to bariatric surgery to assist with weight loss and resolution of obesity-related comorbidities. The three most commonly utilized bariatric procedures are the roux-en-y gastric bypass (RYGB), adjustable gastric band placement, and sleeve gastrectomy. While the RYGB was historically the most commonly performed procedure, laparoscopic sleeve gastrectomy is rapidly gaining popularity, accounting for 0.9% of bariatric procedures in academic centers in 2008 to 36.3% in 2012 . According to the American Society for Metabolic and Bariatric Surgery (ASMB), laparoscopic sleeve gastrectomy is now the most commonly performed bariatric surgery in the United States as of 2013 .

Sleeve gastrectomy was first described as part of a biliopancreatic diversion with duodenal switch in 1998 and was performed laparoscopically in 1999. It was first done as a stand-alone procedure in 2003 as part of a two-stage weight loss procedure and was recognized by the ASMBS as an acceptable option for primary bariatric surgery in 2009. The procedure is most commonly performed using a linear cutting stapler to form the gastric sleeve. The most concerning complications from this procedure include staple-line leak and hemorrhage, which occur in 2.8 and 3% of patients overall, respectively. Multiple studies have been conducted to determine how to reduce complication using staple line analogs, such as oversewing with suture, using bovine pericardium, applying liquid hemostatic matrices, and using an absorbable polymer membrane (GORE SEAMGUARD Reinforcement, W. L. Gore & Associates, Elkton, MD). In a recent study, the absorbable polymer membrane was found to have lowest leak and overall complication rate.

There are two main manufacturers of laparoscopic linear cutting staplers that are Food and Drug Administration-approved for use in laparoscopic sleeve gastrectomies, and both have options for absorbable polymer membrane reinforcement. These companies are the Covidien with iDrive™ Ultra Powered Stapling System and Endo GIA™ Reinforced Reload with Tri-Staple™ Technology (Covidien, Dublin, Ireland) and Ethicon with the Echelon™ Stapler (Echelon Flex™ Powered Endopath® Stapler; Ethicon Endo-Surgery Inc., Cincinnati, OH, USA), which is compatible with GORE SEAMGUARD for reinforcement. While a study with 26 patients incidentally found no difference in outcomes between the two devices without an absorbable polymer membrane, to our knowledge there is no non-industry-funded study designed to compare intra-operative findings and outcomes in sleeve gastrectomy between the two devices with absorbable polymer membranes. We hypothesize that the sleeve creation time and time needed to load each staple cartridge will be different between the two devices

## **5.2 Scientific Justification:**

Linear cutting staplers function by firing six rows of staples and then cutting with three on each side. Depending on the manufacturer, the staple height and method of firing differs. The staple height affects the ability to achieve hemostasis and tissue approximation. Currently there are two manufacturers of such FDA-approved devices, neither of which has any proven superiority for sleeve gastrectomies. This study would help us decide if we can provide better patient care by using a particular device.

## **5.3 Human Use Justification:**

This research involves no deviation from standard of care for a common human surgery. In order to fairly assess outcomes in human patients, the data must be from human subjects.

## **6. PLAN SECTION**

### **6.1. New Investigational Drugs/ Investigational Devices Exemption Status:**

N/A

#### **6.1.1. Exemptions for an Investigational New Drug (IND) application to the FDA:**

N/A

## **6.1.2. Studies under an Investigational Device Exemption (IDE) or are Exempt from an IDE Requirement:**

N/A All devices in the study are already FDA approved for the intended study purpose. Please see 510K and labeling information included with the submission.

## **6.2 Selection of Subjects**

### **6.2.1 Type of the Subject Population:**

New bariatric patients who have already opted to pursue a sleeve gastrectomy will be invited to enroll in the study in the bariatric clinic during their pre-operative visit.

### **6.2.2 Inclusion and Exclusion Criteria**

#### **a. Inclusion Criteria (*justify the inclusion of subjects who may be vulnerable; i.e., pregnant women, children, decisionally impaired that require proxy (LAR) consent, enlisted Soldiers, etc.*)**

- a. Informed consent obtained and signed from each subject,
- b. Age  $\geq$  18 years
- c. Requirement for agreement to avoid conception
- d. BMI  $>40$
- e. BMI  $>35$  with obesity-related co-morbidity
- f. Pre-operative psychiatric evaluation
- g. Pre-operative laboratory studies that fail to demonstrate secondary cause of obesity
- h. Pre-operative upper endoscopy performed with biopsy
- i. Full course of triple therapy for patients with *Helicobacter pylori* on EGD

#### **b. Exclusion Criteria (*Explain if a specific population is being excluded and provide a justification for doing so*)**

- a. Pregnancy- Patients are not eligible for bariatric surgery, and if they become pregnant after surgery, they would present confounding variables and alter weight loss
- b. Tobacco use within one month of surgery or any time within study period- Most staff will not perform bariatric surgery on active smokers as it negatively impacts healing
- c. Prior bariatric surgery- Makes repeat bariatric surgery more difficult and could increase risk of complications
- d. Inflammatory bowel disease- Rare diagnosis that may increase chance of complications, thus confounding results
- e. Active duty military- Not eligible for bariatric surgery

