## **2.4 Methodology / Technical Approach (including the number of subjects/records to be studied):**

New bariatric patients who have elected for a sleeve gastrectomy as part of standard of care will be invited to participate in the study during the bariatric clinic at William Beaumont Army Medical Center. Patients who meet the inclusion criteria will be invited to participate in the study. Please see Section 6.2.3 for specific details on study recruitment and Section 6.2.4 for specific details on the consent process. These patients will be consented in the bariatric clinic by a research resident listed on the protocol.

Three folders will be made, one for each bariatric surgeon, and 25 Covidien cards and 25 Ethicon cards will be placed into each for a total of 150 patients. All bariatric surgeons are trained and familiar with both devices. Once consented, a card will be removed at random to determine which stapler will be used. Bioabsorbable staple line reinforcement will be utilized with both staplers. Once in the operating room, the case start time, time from first staple firing to completion of sleeve, total stapler loads required, number of staple misfires, character of any staple line bleeding, and time for tech to load each cartridge will be recorded on a data collection sheet by a research resident, listed as an associative investigator on this protocol. The subject's post-operative course will follow the bariatric protocol. During follow-up, they will be monitored for weight loss, post-operative complications, and any other required interventions. This information will be obtained by reviewing the subject's medical record after follow-up appointments. Per the bariatric protocol, subjects will follow-up as noted in 6.3.5. If a patient withdraws consent for the study prior to surgery, they will still receive surgery and perioperative treatment in line with institutional protocol, and they will be withdrawn and create a vacancy for a new subject. If a patient withdraws consent after surgery, we will cease logging data for the study on that subject. We will clarify whether they want all data to be removed from the study or if they simply want no more data to be entered into the study and abide by their wishes, and they will remain in the original randomized group in accordance with intention-to-treat principles.

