**6.3.2 Study Methodology/Procedures:**

Patients who express an interest in bariatric surgery will attend a bariatric seminar and initiate the process of scheduling bariatric surgery per department protocol. Once qualified for surgery, the patients will present to bariatric clinic, which takes place in the general surgery clinic on Tuesdays, and have a one-on-one discussion about their desired surgery with a staff physician. If the patient desires a sleeve gastrectomy, the study will be discussed. Consent will be obtained, and the patient will be randomized into the Covidien or Ethicon group. The subject will proceed with surgery per department protocol. In the operating room, a data collection sheet will be available in the operating room to make note of time for creation of sleeve from first firing to completion, total number of staple loads fired, number of misfires, character of any bleeding at the staple line and which interventions were required to control it, and time it takes for the surgical technologist to reload the stapler. At William Beaumont surgical technologists are trained on loading each linear cutting stapler by the Covidien and Ethicon representatives. We will still ensure at the start of the case they are familiar with loading the provided device. No additional training for device will be mandated, as surgical technologist turnover would make this difficult to provide equal training, and it would detract from internal and external validity, since we do not normally provide extra training. Typically the sleeve is created by staff or higher level residents (PGY-2 and above). However, all residents are trained on the devices and are therefore capable of creating the sleeve with close staff supervision, as is standard for our institution. For the purpose of this study, we intend on maintaining this practice since all level residents may be assisting and performing this surgery throughout their residency and deviation would lead to questionable internal validity. After surgery, patients will be admitted to the hospital, and care will follow the department's bariatric protocol. Once discharged, they will follow-up at 3 weeks, 6 weeks, 3 months, 6

months, and then annually. Subjects will be followed for 1 year after surgery. During that time, weight loss, presence of staple line leaks, any readmissions, and any other interventions will be monitored.

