#### **6.4.2 Data analysis:**

For the continuous primary endpoints, the two-sample t-test for 2 means will be used to compare the 2 Devices at Surgery. For the continuous secondary endpoints, such as weight loss, the General Linear Mixed Model Analysis for repeated measures over time will be used to test for the Device effect, Time effect and the Device by Time Interaction. For the binary secondary endpoints (Yes/No), such as Staple line leak, Readmission or ER visits, further sleeve interventions, over time, the General Estimating Equations (GEE) analyses will be used to test for Device effect, Time effect and the Device by Time Interaction. For all tests, the level of significance is set at 0.05.

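### The tobacco exclusion runs through follow-up, so as written it can remove randomised, operated patients for a later event, and no analysis set prevents this

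*Combined protocol and SAP*

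**What the plan says.** Section 6.2.2 b (Exclusion Criteria) lists "Tobacco use within one month of surgery or any time within study period". The reason given is pre-operative: most staff would not operate on an active smoker, because smoking impairs healing. The same list excludes pregnancy, and part of its justification looks past surgery: "if they become pregnant after surgery, they would present confounding variables and alter weight loss". Section 6.2.2 a separately includes "Requirement for agreement to avoid conception".

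On timing, Section 6.3.2 says "Consent will be obtained, and the patient will be randomized into the Covidien or Ethicon group", then surgery takes place, and "Subjects will be followed for 1 year after surgery".

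On who is analysed, Section 6.4.2 says that for the continuous primary endpoints "the two-sample t-test for 2 means will be used to compare the 2 Devices at Surgery". It names mixed-model and GEE analyses for the secondary endpoints over time. Neither 6.4.2 nor 6.4.3 defines an analysis population. Intention-to-treat appears once, in Section 2.4, for patients who withdraw consent after surgery: "they will remain in the original randomized group in accordance with intention-to-treat principles". The same sentence provides for data removal at the patient's wish: "We will clarify whether they want all data to be removed from the study". Patients who withdraw before surgery are replaced.

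**The concern.** An eligibility criterion should be decidable before the patient is treated. The second half of the tobacco criterion is not, because it can be met months after the operation. Applied at that point, an exclusion can act only by taking the patient out.

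Two harms follow. First, sleeve creation time, the percentage of firings with technical difficulties, cartridge load times and staple-line bleeding are all recorded in the operating room. Smoking or conceiving later cannot affect them, so removal throws away valid data for no gain.

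Second, leak, readmission or emergency visits, further sleeve interventions and weight accrue over the following year. The protocol itself links smoking to poor healing. The data list in 6.3.4 has no tobacco item, so later use would come to light mainly through charts and clinical contacts. Patients with complications plausibly have more of these, although the documents give no figure for it. Removal could then be related to outcome. With no rule written down, the decision could also be taken after outcomes are known, by staff who record the operative data and may know the device. These comparisons carry weight: Section 6.4.4 would abort the study on a difference in complications, and the Abstract puts clinical outcomes ahead of cost when choosing a device.

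**Working it through.** **Step 1: sequence of events.** Consent, card draw, surgery, then one year of follow-up (2.4, 6.3.2). Tobacco use in the month before surgery can be known by the day of surgery. Tobacco use in the year after surgery cannot. The second half of the criterion therefore reaches patients whose primary data already exist.

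**Step 2: is there an overriding rule?** Section 6.4.2 names tests but no population. Section 6.4.3 gives numbers only. Section 2.4 covers consent withdrawal only. None limits the tobacco criterion to baseline or keeps a later smoker in the analysis.

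**Step 3: reproduce the sample size (6.4.3).** Inputs: effect size d = 0.5, two-sided alpha 0.05, power 80%.
- Normal approximation: n = 2(1.960 + 0.842)² / 0.5² = 62.8, so 63 per arm.
- Noncentral t: n = 63.77, so 64 per arm. This is the plan's figure.
- Adding 11 gives 75. The allowance is 11/75 = 14.7%.

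**Step 4: power if patients are removed.** Noncentral t with 2n − 2 degrees of freedom and noncentrality 0.5 × √(n/2), which is 3.06 at n = 75 and 2.83 at n = 64. The documents give no rate of later tobacco use or pregnancy, so the loss is an assumed range.

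| Removed per arm (assumed) | n left of 75 | Power at d = 0.5 |
|---|---|---|
| 0% | 75 | 86.0% |
| 5% | 71.25 | 84.2% |
| 10% | 67.5 | 82.2% |
| 14.7% | 64 | 80.1% |
| 20% | 60 | 77.5% |
| 30% | 52.5 | 71.8% |

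If other attrition has already used the full allowance, removing a further 5%, 10%, 15% or 20% of the 64 leaves 78.1%, 75.8%, 73.4% or 70.7%.

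**Step 5: sparse events.** Section 5.1 gives an overall leak rate of 2.8%, and 75 × 0.028 = 2.1 expected leaks per arm. If removal were independent of leak, the expected number of leaks lost per arm would be 2.1 × 0.05 = 0.1 to 2.1 × 0.15 = 0.3 over an assumed 5% to 15% removal. If removal is related to complications the loss is larger. In the worst case, one removed patient with a leak takes away about half of an arm's expected count (1/2.1 = 48%).

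**The case against.** The strongest defence is that no section says an operated patient's data will be dropped. The stated reason for the tobacco exclusion is pre-operative, 6.3.4 collects no tobacco or pregnancy item, and the only named pregnancy test in 6.3.5 is among the pre-operative labs. No removal procedure has been set up. That is correct: removal is inferred from the wording. But the wording of the tobacco criterion is explicit, chart review could reveal later use, and nothing tells the analyst to keep the patient.

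A reader might infer four stronger points that the documents do not support.

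- *That pregnancy after surgery is itself an exclusion criterion.* The criterion is pregnancy. The post-operative element is only in its justification, and later conception is addressed by the agreement required at enrolment.
- *That the plan contradicts a general intention-to-treat commitment.* It makes none. Its one sentence concerns consent withdrawal and itself provides for full data removal. This is a gap in the plan, not a contradiction.
- *That bleeding would be selectively removed through late discovery.* The bleeding endpoint is recorded in the operating room, so late discovery does not select on it. The loss there is needless but has no such link to outcome.
- *That bias between the devices is certain.* Neither device has a stated route to smoking or conception. Distortion between arms would require complications to differ by device and discovery to depend on complications.

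An obvious remedy also needs care. Ending the exclusions at the card draw would cut short the one-month pre-operative tobacco window. Requiring every randomised patient to be analysed would conflict with the replacement and data-removal provisions in 2.4.

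**Conclusion.** The point holds for the tobacco criterion, which as written can remove patients for an event after randomisation. The pregnancy rationale leaves the same reading open, with less force. The absence of a defined analysis set means nothing in the plan settles either case.

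The main cost is to the randomised comparison, not to power. Total losses up to 14.7% per arm stay within the attrition allowance at 80.1% power; power falls below 80% only if removals come on top of full attrition or exceed about 15%. The comparisons most exposed are leak, readmission or emergency visits, further interventions and weight, and for leak only about 2 events per arm are expected. These sizes rest on the protocol's 2.8% leak rate, d = 0.5 and assumed removal rates. Removal linked to outcome is a plausible risk that the documents neither quantify nor rule out. The change should be made before analysis.

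**What to change.** 1. In 6.2.2 b, delete the part of the tobacco criterion that extends through the study period as a reason for exclusion from the study or analysis. State that the tobacco and pregnancy exclusions apply only to status up to surgery. Leave the existing pre-operative window and surgical eligibility as they are.
2. In 6.4.2, define the analysis set: all randomised patients who undergo surgery, analysed by assigned device for every endpoint regardless of later tobacco use or pregnancy, subject to the withdrawal, replacement and data-removal provisions in 2.4.
3. For weight only, add a supportive mixed-model analysis that sets weights recorded after a charted pregnancy to missing.

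The cost is protocol wording, one supportive analysis and noting pregnancy from the chart review already planned. The main weight analysis will be slightly noisier. No extra patients are needed.
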